## Lay Summary

1 \* Provide a summary of the background and purpose of the study in language that can be understood by a person without a medical degree.

The purpose of the current study is to evaluate the effects on child and family development of early community services, including a community-wide nurse home visiting program, Maryland Family Connects. The proposed study will be conducted in partnership with [REDACTED] and Sinai Hospital, both located in Baltimore, MD. For the purposes of this study, Sinai Hospital will serve as the community/catchment area. [REDACTED] is the provider of the Maryland Family Connects (MFC) program. Nurse home visitors from [REDACTED] currently offer MFC to all Baltimore City residents who give birth at Sinai Hospital. Nurse home visitors enroll these new mothers into MFC while they are still in the hospital/maternity ward and with post-discharge outreach. Following Dodge et al. (2013; 2014) when the current study, [REDACTED] officially begins, nurse home visitors will recruit new mothers into the study every other day only (on odd dates). [REDACTED] staff will recruit all Baltimore City residents who give birth at Sinai Hospital, regardless of odd/even birth date, while they are still in the hospital/maternity ward and with post-discharge outreach.

Study outcomes will include family service receipt and children's connection to a medical home, maternal psychosocial wellbeing, home safety, and child maltreatment. One research assessment, consisting of a 60-minute in-home (when possible) or virtual interview, will occur when infants are approximately 6 months old. Mothers will also be asked for permission to access and analyze (a) their child's official birth records; (b) records from Sinai Hospital and/or the Maryland Department of Health; (c) records from the Maryland Department of Human Services; (d) records from the Maryland Family Connects program; and (e) records from the Maryland State Department of Education, all of which will be reviewed for child health and family service needs and receipt until the target child is 6 years of age.

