## Supporting Literature

1 \* **Provide a summary of current literature related to the research: *If you uploaded a separate research protocol document in the 'Research Protocol' page, cite the applicable section and page numbers from that document in the answer box below.***

Family Connects is a universal nurse home visiting program designed by Dodge and colleagues at Duke University (Dodge et al., 2013; 2014). Family Connects is the first program of its kind to be implemented on a community-wide scale. Family Connects was developed as a brief, universal, postnatal nurse home visiting intervention intended to screen for risk, provide brief intervention, and connect families with more intensive evidence-based services as needed. Family Connects is not intended to be a substitute for intensive programs or services, but is meant to serve as a universal screening to ensure that families are matched with services within their own communities that most appropriately meet the identified needs. A primary goal of Family Connects is to reduce the incidence of infant injury and use of emergency medical care in the first year of life.

Family Connects is available to every family in the designated catchment area. Once screening has occurred, however, families with higher needs are triaged and referred to appropriate services.

Family Connects is highly structured and consists of 3 to 7 scripted in-person or telephone contacts, with the first contact is at the hospital immediately following the infant's birth followed by 1 to 3 nurse home visits when the child is 3 to 8 weeks old, 1 or 2 nurse contacts with community service providers and/or maternal and infant health care providers, and an in-person or telephone follow-up conversation 1 month later.

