During the home visits, the nurse establishes rapport with the mother (and father or other family members, when possible), provides brief education about infant care, parenting and child development (organized as 20 "teaching moments"), and assesses health and psychosocial risk in each of 12 domains: parenting/childcare (child care plans, parent-infant relationship, and management of infant crying), family safety (maternal supports, family violence, past maltreatment), parent mental health (depression/ anxiety, substance abuse, emotional support), and health care (parent health, infant health, and health care plan). A score of 1 (low risk) in a particular area requires no further intervention. With a score of 2 (moderate risk), the nurse delivers a brief intervention on the topic, usually consisting of 1 to 3 sessions. For a score of 3 (high risk), the nurse uses motivational interviewing – an evidence-based approach to behavioral change – to connect the family with community resources appropriate to meet the identified need (e.g., mental health counseling, financial resources or treatment for substance abuse). A score of 4 (imminent risk) requires emergency intervention. The nurse makes a final visit or phone call 4 weeks after completing the case, to reinforce community connections.

Dodge and colleagues randomly assigned every (even /odd) hospital birth in Durham County, North Carolina over a period of 18 months (N = 4777). They reported a Family Connects participation rate of 80% of the community population of families of newborns and 84% fidelity to the Durham Family Connects protocol. Hospital records were analyzed using an intent-to-treat approach to evaluate impact among a representative subset of 549 families.

Dodge et al. (2013) found that families assigned to intervention had 50% less total emergency department use across the first 12 months of life, controlling for demographic factors. They concluded that nurse home visiting can be implemented universally at high fidelity with positive impacts on infant emergency department usage that are similar to those of longer, more intensive home visiting programs. This approach was viewed as offering a novel solution, achieving population-level impact through an individually tailored intervention.

The proposed study will be the first RCT of the Family Connects program outside of Durham, NC.

2 **If available, upload your applicable literature search:**

Name	Created	Modified Date

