## Study Procedures

**If you uploaded a separate research protocol document in the 'Research Protocol' page, cite the applicable section and page numbers from that document in the answer boxes below. (If this study is a collaborative UM/VA study please list each procedure that is being conducted and the locations where it is being conducted.)**

1 \* Describe all procedures being performed for research purposes only (these procedures would not be done if individuals were not in the study) and when they are performed, including procedures being performed to monitor subjects for safety or to minimize risks:

Research staff will visit the Sinai Hospital maternity ward on a daily basis. They will receive regular updates from maternity and MFC staff about new births to Baltimore City residents. For approximately one year and a half starting July 15, 2019, all Baltimore City residents who give birth on an odd date at Sinai Hospital will be offered MFC by nurse home visitors employed by [REDACTED]. From July 15, 2019 – January 14, 2021, research staff will approach ALL new mothers (Baltimore City residents giving birth on even or odd dates) within 1-3 days of the birth of the baby, while they are still in the hospital/maternity ward. The researchers will provide mothers with a brief description of the study and a 1-page information sheet (attached). The researchers will request permission to contact the mothers when their infants are approximately 6 months old to schedule the in-home psychosocial interview. During the hospital meeting, the researchers will confirm mothers' contact information and share their own contact information.

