The psychosocial interview will assess the domains of infant health care, maternal wellbeing, maternal adverse childhood experiences, maternal adult attachment security, use of community services, including child care, neighborhood collective efficacy (community support), and quality of the home environment, including home safety and supportive parenting by both mothers and fathers (including non-resident fathers). Basic demographic questions will also be asked. Wherever possible, we will use standardized and widely used research assessments (e.g., the Edinburgh Postpartum Depression Scale, the 10-item Adverse Childhood Experiences (ACEs) questionnaire, the Home Observation Measurement of the Environment [HOME] assessment). The principal research assistant (typically RA #1) will administer all assessments via structured interview, with responses recorded on a secure electronic tablet. RA #1 will complete the following steps before administering the ACEs questionnaire: 1. Briefly explain what ACEs are and why they are important to understand; 2. Remind participants that their scores are private, but if we learn that an experience of childhood maltreatment was not reported, we will be legally obligated to consult appropriate authorities about the possibility of making a report; 3. Remind participants that they can stop at any point, refuse to respond, or talk about how they are feeling; 4. Remind participants that we are providing all participants with a list of mental health resources, including the phone number for a 24-hour parent hotline staffed by [REDACTED]. In addition, per HOME protocol, the principal research assistant will observe, rate, and record several qualities of the home environment and the mother's parenting behaviors.

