For in-home interviews, written consent will be obtained in the participant's home at the 6-month research assessment. For virtual interviews, verbal consent will be obtained through the virtual interviewing platform before the 6-month research assessment begins.

7 \* Describe the provisions for assessing participant understanding:

Research staff will be bachelor-level or higher and will receive training in assessing participant understanding. Research staff will obtain verbal confirmation of understanding from participant in addition to signed written consent for in-home interviews and verbal consent for virtual interviews. Each participant will be allowed to ask questions. The consent form is written at a 9th grade reading level to make sure that it will be comprehensible to participants with a wide range of education levels. The only portion of the consent that is not at this reading level is wording required by the UMB IRB.

8 \* Describe the consideration for ongoing consent:

Given the single assessment point, ongoing consent is not required.

ID: VIEW4E1C661D0AC00  
Name: v2\_Informed Consent Process

View: v2\_Waiver of Documentation of Consent

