Effects of Early Community Services on Child and Family Development

ClinicalTrials.gov Identifier: NCT04019977

Last updated: July 18, 2023

Statistical Analysis Plan

The principal independent variable will be MFC group (MFC participant/non-participant). The dependent variables of interest will be (a) infant emergency room use and overnight hospital stays; (b) family use of community resources and child care; (c) maternal wellbeing; and (d) quality of the home environment. We will also explore long-term differences between MFC and non-MFC participants in (a) rates of official investigations for child maltreatment and (b) two indicators of early educational achievement: kindergarten readiness scores and rates of kindergarten attendance.

A two-tailed intent-to-treat design analysis will include all randomly assigned families (regardless of actual intervention participation). Ordinary least squares regression models will be used to estimate impact of MFC on continuous and categorical outcomes. Poisson regression models will be used for count variables with skewed distribution. Covariates for all models will include the following: Medicaid status (yes/no) at birth and at 6 months, mother race/ethnicity (nonminority/minority), single parent household (yes/no), birth complications (yes/no) including maternal health conditions affecting the baby, infant injuries from birth trauma, and infant distress. Exploratory moderators will include infant birthweight, family Medicaid status, and mothers' adverse childhood experiences and adult attachment security. All results will be analyzed at the .05 significance level.

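### Adult attachment security is listed as a moderator of the MFC effect, but its only described measurement comes after the programme contacts, so effects within its levels may not be randomised comparisons

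*SAP*

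**What the plan says.** The second paragraph of the SAP, repeated in the protocol under Sample Size and Data Analysis, lists four moderators: "Exploratory moderators will include infant birthweight, family Medicaid status, and mothers' adverse childhood experiences and adult attachment security". It does not say when each is measured, or whether attachment would be split or kept continuous.

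The protocol places attachment in the interview (Study Procedures, item 1): "The psychosocial interview will assess the domains of infant health care, maternal wellbeing, maternal adverse childhood experiences, maternal adult attachment security". The Lay Summary gives the timing: "One research assessment, consisting of a 60-minute in-home (when possible) or virtual interview, will occur when infants are approximately 6 months old". The Informed Consent Process section confirms that there is no other occasion: "Given the single assessment point, ongoing consent is not required".

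The programme comes earlier. Under Supporting Literature, the hospital contact is "followed by 1 to 3 nurse home visits when the child is 3 to 8 weeks old", and the last scheduled step is "an in-person or telephone follow-up conversation 1 month later".

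**The concern.** Assignment by birth date makes the arms comparable within groups defined by characteristics that MFC cannot have changed. It gives no such guarantee within groups defined by something measured after the programme and possibly altered by it. If MFC moves some mothers from less secure to more secure, the mothers called secure in the MFC arm are a different mix from those called secure in the control arm. The same holds for a continuous interaction term.

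The documents make such a change conceivable. The nurse's risk domains include the parent-infant relationship, maternal supports and "parent mental health (depression/ anxiety, substance abuse, emotional support", with brief intervention or referral when risk is scored above the lowest level. The protocol also hypothesises better maternal wellbeing. At stake is how an exploratory finding may be read: as a randomised subgroup effect, or as an association.

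**Working it through.** **Timing**

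- Home visits: infant age 3 to 8 weeks (Supporting Literature).
- Follow-up one month later, about 4 weeks: 3 + 4 = 7 and 8 + 4 = 12, so contacts end at roughly 7 to 12 weeks.
- Attachment: about 6 months, or 26 weeks.
- Hospital contact by research staff: "The researchers will request permission to contact the mothers when their infants are approximately 6 months old to schedule the in-home psychosocial interview". It otherwise introduces the study and exchanges contact details; no psychosocial measure is described.
- Records to be accessed (birth, hospital or health department, human services, MFC, education): none is described as holding attachment security.

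On the documents, attachment is therefore measured only after the programme.

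**Scale**

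The protocol gives 400 participants in equal groups, power of at least 0.80 and significance level 0.05, but describes the effect only as small to medium. The sample size therefore cannot be strictly reproduced. Inverting it with the SAP's two-tailed test gives (1.96 + 0.84) × √(2/200) = 0.28 SD, which fits that description. I use 0.28 as the assumed true effect.

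**Illustration (all inputs assumed)**

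Let S be security without MFC (standard normal), b its association with the outcome (0.3 to 0.5), and T the assigned arm. MFC raises measured security M by δ, so M = S + δT. The outcome is Y = 0.28T + bS + error.

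*Median split at the control median, δ = 0.2*

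- Share secure: Φ(0.2) = 58% with MFC, against 50% in controls.
- Mean S among secure mothers: φ(0.2)/Φ(0.2) = 0.391/0.579 = 0.675 with MFC; φ(0)/0.5 = 0.798 in controls.
- Mean S among insecure mothers: −0.391/0.421 = −0.929 with MFC; −0.798 in controls.
- Effect among secure mothers: 0.28 + b(0.675 − 0.798) = 0.24 at b = 0.3 and 0.22 at b = 0.5.
- Effect among insecure mothers: 0.28 + b(−0.929 + 0.798) = 0.24 at b = 0.3 and 0.21 at b = 0.5.

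The loss is 0.04 to 0.07 SD in each stratum. The false interaction, b × [(0.675 − 0.798) − (−0.929 + 0.798)], is below 0.01 SD. A simulation of 4 million families per scenario also gave stratum effects of 0.21 to 0.24.

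*Other shifts, same formulas*

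| δ | Secure, MFC v control | Effects within strata | False interaction |
|---|---|---|---|
| 0 | 50% v 50% | 0.28 | 0 |
| 0.2 | 58% v 50% | 0.21 to 0.24 | below 0.01 |
| 0.5 | 69% v 50% | 0.11 to 0.19 | 0.02 to 0.03 |

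If only insecure mothers shift, the false interaction is 0.01 to 0.02 at a 0.4 SD shift and 0.07 to 0.11 at 1.0 SD. With a cut at the control median, what matters is how many mothers cross it.

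*Kept continuous*

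Substituting S = M − δT gives Y = (0.28 − bδ)T + bM + error. The effect at a given M falls by bδ, which is 0.06 to 0.10 at δ = 0.2. There is no T × M term, so a uniform shift creates no false interaction; a shift that varies with S would.

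**Benchmark for an interaction**

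With four cells of 100, the contrast detectable at 80% power is (1.96 + 0.84) × √(4/100) = 0.56 SD.

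**Medicaid**

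The SAP's covariate list has Medicaid status both at birth and at 6 months, while the moderator carries no date. A 6-month value would raise the same timing question; the value at birth would not.

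**The case against.** The case against has real weight. The moderators are labelled exploratory, and no confirmatory subgroup claim is planned. Adult attachment may be a fairly stable trait. It is not one of the nurse's 12 domains or a hypothesised outcome, and the parent-infant relationship is a different construct. The nurse assesses risk in those domains, and a low score leads to no further intervention. The 0.2 SD is an arm-level shift with decliners included; at the 80% participation cited from the earlier trial it means 0.2/0.80 = 0.25 SD among participants, which is a good deal for a brief programme.

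These points limit the likely size, but they do not change the order of measurement. Neither document argues that attachment is stable, compares it by arm, or limits how the interaction is to be read.

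A reader might infer more than the documents support:

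- *That the result would misdirect targeting of the programme.* Targeting depends on the difference between strata. A similar loss in each leaves that difference almost unchanged, and the false interaction with a 0.4 SD shift confined to insecure mothers (0.01 to 0.02 SD) is far below the 0.56 SD the trial could detect.
- *That current mood contaminates a self-reported score.* No attachment instrument is named. Shared mood would also make the arms non-comparable only if MFC changed mood or reporting.
- *That adverse childhood experiences fail in the same way.* They are collected at 6 months but concern the mother's childhood, so MFC could alter only recall or reporting.

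**Conclusion.** The point holds as a limit on interpretation. Attachment security is a planned moderator measured only after the programme, so its interaction with MFC cannot be read as a randomised subgroup effect without assuming that MFC leaves it unchanged.

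The size is unknown. It is nil if that assumption is true. With a 0.2 SD shift and an association of 0.3 to 0.5, a true 0.28 SD becomes about 0.21 to 0.24 SD in median-split strata. Attenuation presumes that MFC raises security and that security goes with better outcomes. Little false interaction arises unless the shift is large or differs strongly between mothers.

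It would be wrong to conclude that MFC does change attachment, or that the main results are at risk from this moderator: the documents show no such change, and the main intent-to-treat contrast does not use attachment.

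**What to change.** This is a cheap improvement. In the SAP's moderator sentence:

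1. Specify Medicaid status at birth.
2. Mark attachment security and adverse childhood experiences as measured at the 6-month interview.
3. Report both by assigned birth-date arm before any moderator result, as differences with confidence intervals. Do not use a pass/fail balance test, because a non-significant difference does not show equivalence.
4. Present the attachment-by-MFC interaction as a descriptive association, and report attachment as an exploratory 6-month outcome as well.

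The cost is a few lines of wording and one table, with no new data and no change in sample size. The sponsor gives up a causal effect-modification reading for one exploratory moderator; the analysis itself can stay.

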## Sample Size and Data Analysis

**If you uploaded a separate research protocol document in the 'Research Protocol' page, cite the applicable section and page numbers from that document in the answer boxes below.**

1 \* Provide the rationale and sample size calculations for the proposed target population:  
Following guidelines established by Cohen (1988) and using Gpower software (Faul et al., 2009), power analyses estimating at least 0.80 power and a significance level of 0.05 indicated that a sample size of 400 (assuming equal groups) will detect small to medium effects in most of the outcomes of interest. Some outcomes are more exploratory in nature. In addition, it is possible that additional research funding garnered in the course of this study will allow for an increased sample size.

2 \* Provide the plan for data analysis. Include in the description the types of comparisons that are planned (e.g., comparison of means, comparison of proportions, regressions, analysis of variance, etc.), which is the primary comparison/analysis, and how the analyses proposed will relate to the primary purposes of the study:  
The principal independent variable will be MFC group (MFC participant/non-participant). The dependent variables of interest will be (a) infant emergency room use and overnight hospital stays; (b) family use of community resources and child care; (c) maternal wellbeing; and (d) quality of the home environment. We will also explore long-term differences between MFC and non-MFC participants in (a) rates of official investigations for child maltreatment and (b) two indicators of early educational achievement: kindergarten readiness scores and rates of kindergarten attendance.

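### Birthweight, a planned moderator fixed before any MFC contact, is not a covariate in the infant emergency-visit and hospital-stay models, which may forgo some precision

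*SAP*

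**What the plan says.** The second paragraph of the SAP and item 2 of the protocol's Sample Size and Data Analysis section carry the same text. The list opens "Covariates for all models will include the following: Medicaid status (yes/no) at birth and at 6 months" and goes on to race/ethnicity, single-parent household and one yes/no item, "birth complications (yes/no) including maternal health conditions affecting the baby, infant injuries from birth trauma, and infant distress". Birthweight is not on it. It appears only in the next sentence: "Exploratory moderators will include infant birthweight". Family Medicaid status is on both lists, so the plan does not treat covariate and moderator as exclusive roles.

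The protocol's Supporting Literature section places the first MFC contact in hospital just after the birth and the home visits at 3 to 8 weeks of age. Birthweight precedes both.

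On size, the protocol says "a sample size of 400 (assuming equal groups) will detect small to medium effects in most of the outcomes of interest". The SAP's main comparison is by assignment: "A two-tailed intent-to-treat design analysis will include all randomly assigned families".

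**The concern.** Birthweight is a continuous baseline measure that the program cannot change, and the plan already expects to use it. If it predicts emergency visits and overnight stays beyond the listed covariates, leaving it out keeps removable variance in the MFC estimate for those outcomes. These outcomes matter most to the program, since the protocol names less infant injury and emergency care in the first year as a primary goal. The existing perinatal covariate is a single yes/no flag that mixes maternal conditions, birth trauma and infant distress, and it does not measure size at birth. An interaction model normally includes the moderator's main effect. Birthweight would then enter the exploratory models but not the models that give the main result, and the plan gives no reason for the difference.

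What is at stake is precision, and adjustment for any chance difference in birthweight between odd-date and even-date births.

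**Working it through.** **Inputs from the documents.** N = 400 in equal groups, power at least 0.80, two-sided 0.05, and Poisson models for skewed counts. No numeric effect size, SD, event rate or strength of birthweight as a predictor is given. Everything about birthweight's strength below is an assumption shown over a range.

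**The plan's own figure.** Without a stated effect, 400 can only be checked backwards. The detectable standardized difference is (1.960 + 0.842) × √(2/200) = 0.280. Going forwards, 0.28 needs 201 per group. This lies between the conventional small (0.2) and medium (0.5), so 400 agrees with the plan's wording.

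**Linear models.** If birthweight has partial correlation r with the outcome, given the listed covariates, residual variance is multiplied by 1 − r².
- Extra families = 400/(1 − r²) − 400
- Detectable difference = 0.2802 × √(1 − r²)
- Power at 0.2802 = Φ(2.802/√(1 − r²) − 1.960)

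| r | r² | Extra families | Detectable difference | Power |
|---|---|---|---|---|
| 0 | 0 | 0 | 0.280 | 80.0% |
| 0.1 | 0.01 | 4.0 | 0.279 | 80.4% |
| 0.2 | 0.04 | 16.7 | 0.274 | 81.6% |
| 0.3 | 0.09 | 39.6 | 0.267 | 83.6% |

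The cost of the extra parameter (8 instead of 7, counting intercept, MFC and five covariates) is √(393/392) = 1.0013, about 0.1% in the standard error.

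**Poisson counts.** Let the mean count be μ and the log-rate slope b per SD of birthweight (sign immaterial), with birthweight roughly normal. Without birthweight in the model, Var(Y)/μ² = 1/μ + (e^(b²) − 1). Adjustment removes about the second term, so the share of variance removed is (e^(b²) − 1)/(1/μ + e^(b²) − 1). Assumed means are 0.3 and 0.8.

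| b (rate ratio per SD) | e^(b²) − 1 | μ = 0.3 | μ = 0.8 |
|---|---|---|---|
| 0.1 (1.11) | 0.0101 | 0.3% | 0.8% |
| 0.2 (1.22) | 0.0408 | 1.2% | 3.2% |
| 0.4 (1.49) | 0.1735 | 4.9% | 12.2% |

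This formula ignores the birth-complications flag. Simulation with a correlated flag in the model gives nearly the same picture: about 0% to 3% at slopes of 0.1 to 0.2, and about 5% to 13% at 0.4. In families, 400/(1 − v) − 400 gives about 12 at v = 3%, 21 at 5% and 60 at 13%.

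**Overdispersion lowers the gain.** With gamma variation of shape 1 the denominator becomes 1/μ + 2e^(b²) − 1. At b = 0.4 the shares are then 0.1735/4.680 = 3.7% and 0.1735/2.597 = 6.7%. Simulations of such counts with robust standard errors and rate ratios up to 1.3 per SD (b = 0.26) gave adjusted-to-unadjusted standard-error ratios of 0.995 to 1.005, which is no material gain.

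**Missing values.** Dropping a share m of families multiplies variance by about 1/(1 − m). A complete-case analysis that loses 1% of families (4 of 400) cancels the gain at r = 0.1. One that loses 3% cancels a 3% Poisson gain.

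**The case against.** The strongest reply is that choosing covariates is a design decision, that the plan prespecifies a set, and that nothing here is an error. Much of this stands.

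- **Bias.** A reader might infer that the omission biases the MFC effect. It does not, if assignment by birth date is as good as random. Chance imbalance is already reflected in the standard error.
- **Prognostic strength.** A reader might infer a demonstrated loss. The documents neither state nor quantify that birthweight predicts these outcomes, and at the weak end of the range the gain is close to nil. Part of any perinatal signal is already carried by the complications flag.
- **Scope.** A reader might infer that birthweight belongs in every model. The reasoning covers only infant emergency visits and overnight stays. No comparable case is made for community resources, child care, maternal wellbeing, the home environment, maltreatment investigations or kindergarten outcomes.
- **Availability.** That birthweight is on file is inferred from its moderator role. No section names its source, and the record access described in the Lay Summary and Study Procedures needs the mother's permission, so some values may be missing.
- **Overdispersion.** Adding birthweight would not resolve excess Poisson variance in general. That needs a robust or dispersion-adjusted standard error and is a separate matter.
- **Timing.** Recruitment was planned to end January 14, 2021, with interviews at about 6 months. On that schedule interview data were complete about two years before the SAP date, so an added covariate must be declared as a late change.

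None of this gives a reason for leaving birthweight out of the two infant-health outcomes. The reply lowers the severity and narrows the fix.

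**Conclusion.** The point holds as a low-severity efficiency suggestion confined to infant emergency visits and overnight stays. A baseline variable that the plan already intends to use, and that MFC cannot affect, is missing from the models giving the MFC effect on those outcomes, without a stated reason.

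The possible gain runs from negligible to modest. For linear models it is about 4 to 40 family-equivalents on 400, or 0.4 to 3.6 points on 80% power, for partial correlations of 0.1 to 0.3. For Poisson counts the variance of the log rate ratio falls by about 0% to 3% at slopes of 0.1 to 0.2 per SD and about 5% to 13% at 0.4, and by less (roughly 4% to 7% at 0.4) if counts are strongly overdispersed. These figures rest on assumed prognostic strengths, assumed mean counts and complete birthweight data.

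**What to change.** In the SAP and in item 2 of the protocol's Sample Size and Data Analysis section, add *infant birthweight (continuous)* to the covariates of the infant emergency-visit and overnight-stay models, and keep it as an exploratory moderator. If the investigators prefer to leave it out, one sentence giving the reason would also settle the point.

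State the source of birthweight and a rule for missing values that keeps every family in the intent-to-treat analysis, for example simple imputation of this baseline covariate without using assignment or outcome.

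The cost is one degree of freedom (about 0.1% in the standard error), the handling of any missing values, and reporting the addition as a dated change to the SAP of July 18, 2023. It should be made before these outcomes are analyzed by assigned group. If they already have been, keep the listed covariates for the main result and report the birthweight-adjusted model as a labelled sensitivity analysis. No new data collection should be needed, provided birthweight is obtained for the moderator analysis as planned.
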